#### 6.5.4 Cycle 1, Day 8 (C1D8) – Begin of Radiation Therapy

Within 3 weeks (+/- 3 days) from craniotomy and tumor re-resection (i.e. Cycle 1, Day 8), the subject will initiate **RT**. RT must be provided at the study site (NYUSoM). Technical details for radiation therapy are provided in Section 5.2.2.

- Prior to initiating radiation therapy on C1D8, adverse event assessment, a symptom-directed physical exam and limited vital signs (temperature, resting blood pressure, pulse, and respiration rate) must be performed.
- All subjects will receive HFRT to a total dose of 45 Gy given as 3 Gy per fraction over 15 fractions. RT must begin 3 weeks (+/- 3 days) after craniotomy and tumor re-resection (i.e., Day 8 of Cycle 1).

#### 6.5.5 Cycle 1, Day 15 (C1D15)

The subject will have the Safety Procedures detailed below performed prior to initiating study treatment with nivolumab 3 mg/kg IV and ipilimumab 1 mg/kg IV. Required assessments and study drug administration windows include  $\pm 3$  days of scheduled visit.

- Adverse event assessment
- Concomitant medication collection
- Symptom-directed physical exam as clinically indicated by the investigator or qualified designee at all mid-cycle visits
- Vital signs: When scheduled at the same visit as other procedures, vital signs should be measured prior to clinical laboratory assessments or research blood sample collection.
  - Weight (can be taken within 3 days of scheduled study drug administration)
  - Temperature, resting blood pressure, pulse and respiration rate.

CONFIDENTIAL

This material is the property of the NYU School of Medicine. Do not disclose or use except as authorized in writing by the study sponsor

- Serum chemistry: sodium, potassium, chloride, bicarbonate, calcium, magnesium, phosphorous, glucose, albumin, creatinine, blood urea nitrogen (BUN), uric acid, ALT, AST, total bilirubin, direct and/or indirect bilirubin, alkaline phosphatase (ALP), lactate dehydrogenase (LDH), amylase, and lipase.
- Hematology: WBC count, 3-cell differential (ANC, monocyte count, lymphocyte count), hemoglobin, hematocrit, platelet count
- T cell subsets (CD3, CD4, and CD8 counts)
- Thyroid stimulating hormone (TSH), free T4
- Pregnancy test (urine or serum  $\beta$ -HCG) for women of child-bearing potential
- Research blood samples. All subjects will have the below research blood samples collected. Note: Research blood samples will be taken at 3 time points: **Cycle 1, Day -29 (pre-dose)**, **Cycle 1, Day -15 (surgery)** and **Cycle 1, Day 15** (end of week 6).

A total of 40 mL (four 10 mL purple top EDTA tubes) of whole blood will be drawn and immediately sent to the below sites:

- One (1) 10 mL tube will be sent to the Center for Biospecimen Research and Development (CBRD) at NYUSoM for acquisition of whole blood, buffy coat, and plasma samples.
- Three (3) 10 mL tubes will be sent to the Immune Monitoring Core (IMC) at NYUSoM and immediately processed for isolation of PBMCs.

**Study Drugs:** Nivolumab and ipilimumab will be administered in an outpatient setting as an IV infusion at the specified doses (for details see Administration of Study Drugs, Section 5.3). The doses of study drug must be adjusted each cycle for changes in body weight of  $\geq 10\%$ . The weight used for dosing can be taken within 3 days of scheduled study drug administration.

#### 6.5.6 **Cycle 1, Day 29 (C1D29) and all subsequent Cycle Day 29 visits (i.e., C2D29, C3D29, etc.)**

The subject will have the Safety Procedures detailed below performed prior to initiating study treatment (nivolumab 3 mg/kg IV). Required assessments and study drug administration windows include  $\pm 3$  days of scheduled visit.

- Adverse event assessment
- Concomitant medication collection
- Symptom-directed physical exam as clinically indicated by the investigator or qualified designee at all mid-cycle visits
- Vital signs: When scheduled at the same visit as other procedures, vital signs should be measured prior to clinical laboratory assessments or research blood sample collection.
  - Weight (can be taken within 3 days of scheduled study drug administration)
  - Temperature, resting blood pressure, pulse and respiration rate.
- Serum chemistry: sodium, potassium, chloride, bicarbonate, calcium, magnesium, phosphorous, glucose, albumin, creatinine, blood urea nitrogen (BUN), uric acid, ALT, AST, total bilirubin, direct and/or indirect bilirubin, alkaline phosphatase (ALP), lactate dehydrogenase (LDH), amylase, and lipase.

CONFIDENTIAL

This material is the property of the NYU School of Medicine. Do not disclose or use except as authorized in writing by the study sponsor

- Hematology: WBC count, 3-cell differential (ANC, monocyte count, lymphocyte count), hemoglobin, hematocrit, and platelet count
- Urinalysis: glucose, blood, pH, specific gravity, ketones, and urine protein

**Study Drug:** **Nivolumab only** will be administered in an outpatient setting as an IV infusion at the specified doses (for details see Administration of Study Drugs, Section 5.3). The doses of study drug must be adjusted each cycle for changes in body weight of  $\geq 10\%$ . The weight used for dosing can be taken within 3 days of scheduled study drug administration.

#### 6.5.7 Cycle 2, Day 1 (C2D1) and all subsequent Cycle Day 1 visits (i.e., C3D1, C4D1, etc.)

The subject will have the C2D1 Safety Procedures detailed below performed prior to initiating study treatment (nivolumab 3 mg/kg IV). Required assessments and nivolumab administration windows include  $\pm 3$  days of scheduled visit.

- Adverse event assessment
- Concomitant medication collection
- Complete physical exam, including neurological exam, and KPS assessment
- Vital signs: When scheduled at the same visit as other procedures, vital signs should be measured prior to clinical laboratory assessments or research blood sample collection.
  - Weight (can be taken within 3 days of scheduled study drug administration)
    - Temperature, resting blood pressure, pulse and respiration rate.
- Serum chemistry: sodium, potassium, chloride, bicarbonate, calcium, magnesium, phosphorous, glucose, albumin, creatinine, blood urea nitrogen (BUN), uric acid, ALT, AST, total bilirubin, direct and/or indirect bilirubin, alkaline phosphatase (ALP), lactate dehydrogenase (LDH), amylase, and lipase.
- Hematology: WBC count, 3-cell differential (ANC, monocyte count, lymphocyte count), hemoglobin, hematocrit, and platelet count
- T cell subsets (CD3, CD4, and CD8 counts) at C2D1, C4D1, C6D1, and C8D1 only.
- Urinalysis: glucose, blood, pH, specific gravity, ketones, and urine protein
- Thyroid stimulating hormone (TSH), free T4
- Contrast-enhanced brain MRI (every 8 weeks, even cycles only, i.e. Cycle 2, Cycle 4, Cycle 6, etc.)
- Research MRI (sodium MRI) (every 8 weeks, even cycles only, i.e. Cycle 2, Cycle 4, Cycle 6, etc.)

**Study Drug:** **Nivolumab only** will be administered in an outpatient setting as an IV infusion at the specified doses (for details see Administration of Study Drugs, Section 5.3). The doses of study drug must be adjusted each cycle for changes in body weight of  $\geq 10\%$ . The weight used for dosing can be taken within 3 days of scheduled study drug administration.

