- The Surgical Study Cohort will open once the Safety Lead-In is completed. Patients in the **Surgical Study Cohort** will undergo craniotomy and tumor re-resection within 2 weeks from the first dose of nivolumab and ipilimumab. Patients will begin HFRT 3 weeks after surgery.

All subjects will receive HFRT to a total dose of 45 Gy, given in 15 consecutive fractions of 3 Gy each fraction.

All subjects will continue to receive nivolumab 3 mg/kg IV every 2 weeks and ipilimumab 1 mg/kg every 6 weeks from day of first nivolumab and ipilimumab administration.

One treatment cycle will be defined as 42 days (6 weeks), corresponding to 3 doses of nivolumab and one dose of ipilimumab.

Nivolumab and ipilimumab administration will continue for all subjects for 2 years or until disease progression, intolerable toxicity, death, or the subject meets another withdrawal criteria as per the Subject Withdrawal guidelines (Section 6.12), whichever comes first. Subjects who are discontinued from study therapy will enter the post-study follow-up phase of the study as per Section 6.10.

All subjects will be evaluated every 8 weeks with radiographic imaging to assess response to treatment. Disease assessments will be made using standard RANO criteria. However, non-traditional iRANO criteria (Appendix 3) may be considered for patient management. Adverse events will be monitored throughout the trial and graded in severity according to the guidelines outlined in the NCI-CTCAE version 4.03.

The investigator shall take responsibility for and shall take all steps to maintain appropriate records and ensure appropriate supply, storage, handling, distribution and usage of trial treatments in accordance with the protocol and any applicable laws and regulations.

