## 6.5 Study Procedures for Surgical Study Cohort

**One treatment cycle will be defined as 42 days**, corresponding to 3 doses of nivolumab (administered every 2 weeks) and one dose of ipilimumab (administered every 6 weeks). If nivolumab and ipilimumab dosing is delayed, the cycle count should be interrupted.

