## 6.6 Efficacy Procedures

### 6.6.1 Contrast-Enhanced Brain MRI

Efficacy assessment consisting of a **contrast-enhanced brain MRI** will be performed **every 8 weeks on study**,  $\pm 7$  days. On-study imaging should follow calendar days (every 8 weeks) and should not be adjusted for delays in cycle starts. Clinicians may repeat response assessment more frequently as clinically indicated.

Tumor assessments for all subjects should continue as per protocol even if dosing is delayed.

**Research MRIs (sodium MRI):** All patients will have a research MRI (sodium MRI) at each efficacy assessment timepoint (i.e., at each contrast-enhanced MRI timepoint corresponding to every 8 weeks on study,  $\pm 7$  days). Research MRIs will be performed on MRI equipment housed at the same NYU facility where patients obtain clinical MRIs.

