### 7.2.2 Main Study Cohort - Phase II trial design

A single-stage design will be utilized to estimate overall survival, with a hypothesized 1yr-OS of 60%= $H_1$  and 35%= $H_0$ . We will enroll 24 patients; this design has a two-sided Type I error of 0.05 and a power of 80%.

For endpoint analyses, one year will be defined as 48 weeks (8 cycles) and two years will be defined as 96 weeks (16 cycles). Patients will be evaluated for radiographic responses by conventional contrast enhanced MRI every 8 weeks. Radiographic response assessments will be determined using RANO criteria for GBM.

1yr-OS and radiographic response rates will be estimated with exact 95% confidence intervals; with 24 patients, a 95% CI will be no more than 0.4 units wide. OS will be determined from the time of treatment initiation until the time of death due to any cause, with OS being censored at last follow-up if the patient remained alive. Patients who were last known to be alive and progression-free will be censored at the latest disease assessment. The Kaplan–Meier curves will be used to summarize OS and to estimate the medians.

PFS is defined as the time between treatment initiation and first occurrence of disease progression or death, and will be censored at last follow-up if the patient remained alive without disease progression. PFS is defined as the time from the first dose of study treatment to the earlier of disease progression or death due to any cause. Patients who initiate alternate anticancer therapy in the absence of documented progression will be censored at the latest disease assessment prior to initiation of such therapy. Patients with no post-baseline disease assessments will be censored at the Cycle 1 Dose 1 date unless death occurred prior to the first planned assessment (in which case the death will be considered a PFS event). The Kaplan–Meier curves will be used to summarize PFS and to estimate the medians.

Overall response rate (ORR) is defined as the proportion of patients who achieve best overall response of complete or partial response at any time after initiation of study treatment (prior to initiation of alternate anticancer treatment). Duration of response is defined as the number of months from the time criteria are first met for either CR or PR, until the first date that PD is objectively documented. The duration of objective response will be summarized descriptively using the Kaplan-Meier method.

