26. Ipilimumab will be administered every 6 weeks ( $\pm$ 5 days of scheduled visit) in an outpatient setting as an IV infusion. The ipilimumab dose will depend on individual body weight. The dose of ipilimumab must be adjusted each dose for changes in body weight of  $\geq$ 10%. Dose adjustments for changes in body weight of <10% will be at the discretion of the investigator. Ipilimumab administration will continue for all subjects for 2 years (96 weeks) or until disease progression, intolerable toxicity, death, or the subject meets another withdrawal criterion per protocol.
27. Contrast-enhanced brain MRI: A contrast-enhanced MRI must be obtained within 21 days of the first dose of study treatment. For the Surgical Study Cohort, a post-operative MRI brain must be obtained within 72 hours from craniotomy and tumor re-resection on C1D-15. For response assessment, a contrast-enhanced brain MRI will be performed 8 weeks after study drug initiation, and then every 8 weeks thereafter. MRIs can be performed within 7 days ( $\pm$ 7 days) of scheduled assessment. On-study imaging should follow calendar days (every 8 weeks) and should not be adjusted for delays in cycle starts. Local reading (investigator assessment) will be used to determine eligibility and for participant management. Response Assessments will be performed on every brain imaging assessment performed on protocol per RANO criteria, although non-traditional iRANO criteria may be used for patient management (see **Appendix 3**).

CONFIDENTIAL

This material is the property of the NYU School of Medicine. Do not disclose or use except as authorized in writing by the study sponsor

28. Research Blood Samples: For all patients, whole blood will be drawn at two time points: At pre-dose C1D-29 (-3 days) and at C2D15(±/- 3 days). Four purple top EDTA tubes (40 mL) will be drawn, one EDTA tube will be sent to the CBRD and three EDTA tubes will be sent immediately to the IMC.
29. Research (sodium) MRI: All subjects must have a research MRI performed prior to C1D1 (within 7 days of study drug initiation) and at every response assessment time point on study treatment (i.e., every 8 weeks after study drug initiation, and then every 8 weeks thereafter). Research MRIs can be performed within 7 days (±7 days) of scheduled assessment. Research MRIs must be performed at NYUSoM.

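### Section 6.5.7 ties the surgical cohort's 8-week MRI to even-numbered cycles, which fall 12 weeks apart; the line conflicts with the calendar schedule in Section 6.6.1 and Appendix 2 and must be reconciled

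*Combined protocol and SAP*

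**What the plan says.** Section 6.5.7, which covers Cycle 2 Day 1 and later Day 1 visits in the surgical cohort, lists "Contrast-enhanced brain MRI (every 8 weeks, even cycles only, i.e. Cycle 2, Cycle 4, Cycle 6, etc" and, on the next line, "Research MRI (sodium MRI) (every 8 weeks, even cycles only, i.e. Cycle 2, Cycle 4, Cycle 6, etc". The opening of Section 6.5 states: "One treatment cycle will be defined as 42 days". It also interrupts the cycle count when dosing is delayed.

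Other parts of the protocol set the imaging interval by calendar:

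- Section 6.1: "All subjects will be evaluated every 8 weeks with radiographic imaging to assess response to treatment". Section 3.1.3 says the same for both cohorts.
- Section 6.6.1: "On-study imaging should follow calendar days (every 8 weeks) and should not be adjusted for delays in cycle starts".
- Appendix 2 (the surgical cohort's schedule of events), footnote 27: "a contrast-enhanced brain MRI will be performed 8 weeks after study drug initiation, and then every 8 weeks thereafter". The table places response MRI in a column headed Week 8+, not under the C1D29 and C2D1 visits.
- Appendix 1 footnote 27 gives the main cohort the same rule.

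**The concern.** The two halves of the Section 6.5.7 line cannot both be carried out. An 8-week interval and an every-second-cycle interval agree only if a cycle lasts 28 days, and this protocol's cycle lasts 42.

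The line is operative. It is the only on-treatment response-MRI instruction in the visit procedures of Section 6.5. The corresponding main-cohort visit lists (Sections 6.4.3 and 6.4.4) carry no MRI line, so only the calendar rule governs there. The risk of scanning by cycle is therefore specific to the surgical cohort.

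Section 3.3 makes median PFS, radiographic response rate and median duration of response secondary endpoints for this cohort, and all three depend on when scans are done. In a cohort of 16, even a few patients scanned on a different interval would blur those estimates. The sodium MRI, an exploratory measure, has the same wording.

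**Working it through.** **Inputs.** Cycle length is 42 days (Section 6.5); Section 7.2.2 agrees, since it equates 48 weeks with 8 cycles and 48 / 8 = 6 weeks. First dose is on C1D-29 (Section 6.5.1), with surgery nominally two weeks later and C1D1 two weeks after surgery, so C1D1 is about week 4. The MRI window is 7 days either side (Section 6.6.1; Appendix 2 footnote 27).

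**Can the stated 8 weeks be reproduced?** Interval = 2 × cycle length / 7. With 42 days this is 84 / 7 = 12 weeks. Only a 28-day cycle gives 56 / 7 = 8 weeks. The figure is not reproduced.

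**Scan dates.** Even-cycle Day 1 of cycle k falls at week 4 + 6 × (k − 1).

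| Even cycle | Week from first dose | Nearest 8-week due date | Gap |
|---|---|---|---|
| 2 | 10 | 8 | 2 weeks |
| 4 | 22 | 24 | 2 weeks |
| 6 | 34 | 32 | 2 weeks |
| 8 | 46 | 48 | 2 weeks |

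Each gap is 14 days against a permitted 7. Using the 3-day visit window to move closer leaves 14 − 3 = 11 days, still outside. Counting the day labels literally (29 days instead of 28) moves the dates by one day and changes nothing.

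These are nominal dates. Section 6.5.2 allows surgery from one week after first dose. That would put C1D1 at week 3 and the even-cycle visits at weeks 9, 21, 33 and 45, with gaps of 1, 3, 1 and 3 weeks. Some visits would then reach the edge of the window, but they would still be 12 weeks apart.

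**Number of scans.** By calendar: weeks 8, 16, 24, 32, 40 and 48, which is 6 by week 48 and 12 by week 96. By even cycle: 4 by week 48 and 8 by week 96.

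**Detection lag.** Assume progression is equally likely at any time between scans and is found only at a scheduled scan. Mean lag is half the interval: 8 / 2 = 4 weeks against 12 / 2 = 6 weeks, a difference of 2.

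That average hides a spread. The two schedules repeat together every 24 weeks. From week 10 to week 34:

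| Progression in weeks | Calendar scan | Even-cycle scan | Difference (weeks) |
|---|---|---|---|
| 10–16 | 16 | 22 | +6 |
| 16–22 | 24 | 22 | −2 |
| 22–24 | 24 | 34 | +10 |
| 24–32 | 32 | 34 | +2 |
| 32–34 | 40 | 34 | −6 |

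Weighted mean: (6×6 − 6×2 + 2×10 + 8×2 − 2×6) / 24 = 48 / 24 = 2 weeks.

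**Check with the protocol's own PFS figure.** Section 3.1.3 quotes a 6-month median PFS with standard therapy, about 26.1 weeks (6 × 30.4375 / 7). With exponential progression times (an assumption), mean lag is 4.1 weeks against 6.1. The first scan at or after the true median is at week 32 by calendar and week 34 by even cycle.

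**The case against.** The strongest reply is that the plan as a whole is not ambiguous. The disputed line itself says 8 weeks; Sections 3.1.3, 6.1 and 6.6.1 say 8 weeks for all subjects; and the surgical cohort's own schedule of events says 8 weeks. A reader of Section 6.5.7 alone might infer that this cohort is meant to be scanned every 12 weeks and so will have progression detected later than the main cohort. The documents do not support that. Later detection follows only if staff schedule by the even-cycle wording against every other imaging passage. That part of the reply stands, so the effect on PFS must be stated as conditional.

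Dose delays are similar. Cycle-tied scans would slip because the cycle count is interrupted, but Sections 6.2.3, 6.2.4 and 6.6.1 all keep tumor assessments on schedule during delays.

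The 2-week average is also an upper-side figure. Section 6.6.1 allows extra assessments when clinically indicated, the response criteria appendix counts clear clinical deterioration as progression, and Section 7.2.2 makes death a PFS event. All of these shorten the lag under either schedule and shrink the difference.

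Finally, the stakes are limited: Section 7 plans no formal PFS comparison between cohorts, and the surgical sample size rests on T-cell pathway induction. This too stands. None of it removes the contradiction, because a visit list that names specific cycles can be followed as written.

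**Conclusion.** Section 6.5.7 contains a genuine internal contradiction: with 42-day cycles, its even-cycle instruction means 12 weeks, not 8, and it conflicts with Sections 3.1.3, 6.1 and 6.6.1 and Appendix 2 footnote 27. It is worth correcting because it sits in the procedures for the cohort's treatment visits.

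If the even-cycle wording were followed, about 4 scans would be done instead of 6 by week 48, and progression would be dated about 2 weeks later on average. That average rests on uniform progression times found only at scheduled scans, and it would be smaller otherwise. Individual differences run in both directions, from about 6 weeks earlier to about 10 weeks later on the nominal dates. The 4-week gap between the two maximum lags (12 − 8) should not be read as the most any patient could be affected.

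Two further inferences are not supported. The documents give no scan interval for the historical 6-month median PFS, so nothing can be said about bias against historical data. OS and the cohort's primary objectives (safety, feasibility and tolerability, with T-cell pathway induction in the synopsis) do not depend on scan timing.

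**What to change.** Reconcile the contrast MRI and sodium MRI lines in Section 6.5.7 with Section 6.6.1 and Appendix 2 footnote 27. One way is to replace the even-cycle wording in both lines with a reference to the calendar schedule stated there, timed from first study drug. The cost is a short text correction; it adds no scans beyond those that Section 6.6.1 and Appendix 2 already require. If surgical-cohort patients have already been scanned by cycle, list the actual scan dates alongside the PFS and response results so that any departure from the 8-week interval is visible.

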#### 6.5.8 Cycle 2, Day 15 (C2D15) and all subsequent Cycle Day 15 cycle visits (i.e., C3D15, C4D15, etc.)

The subject will have the C2D15 Safety Procedures detailed below performed prior to initiating study treatment. Required assessments and nivolumab administration windows include  $\pm 3$  days of scheduled

CONFIDENTIAL

This material is the property of the NYU School of Medicine. Do not disclose or use except as authorized in writing by the study sponsor

visit. For administrative purposes, ipilimumab administration can be  $\pm 5$  days of the scheduled administration day.

- Adverse event assessment
- Concomitant medication collection
- Symptom-directed physical exam as clinically indicated by the investigator or qualified designee at all mid-cycle visits
- Vital signs: When scheduled at the same visit as other procedures, vital signs should be measured prior to clinical laboratory assessments or research blood sample collection.
  - Weight (can be taken within 3 days of scheduled study drug administration)
  - Temperature, resting blood pressure, pulse and respiration rate.
- Serum chemistry: sodium, potassium, chloride, bicarbonate, calcium, magnesium, phosphorous, glucose, albumin, creatinine, blood urea nitrogen (BUN), uric acid, ALT, AST, total bilirubin, direct and/or indirect bilirubin, alkaline phosphatase (ALP), lactate dehydrogenase (LDH), amylase, and lipase.
- Hematology: WBC count, 3-cell differential (ANC, monocyte count, lymphocyte count), hemoglobin, hematocrit, and platelet count
- T cell subsets (CD3, CD4, and CD8 counts) at C2D15, C4D15, C6D15, and C8D15 only.
- Urinalysis: glucose, blood, pH, specific gravity, ketones, and urine protein
- Thyroid stimulating hormone (TSH), free T4
- Pregnancy test (urine or serum  $\beta$ -HCG) for women of child-bearing potential

**Study Drugs:** Nivolumab and ipilimumab will be administered in an outpatient setting as an IV infusion at the specified doses defined in the Safety Lead-In or the phase II trial (for details see Administration of Study Drugs, Section 5.3). The doses of study drug must be adjusted each cycle for changes in body weight of  $\geq 10\%$ . The weight used for dosing can be taken within 3 days of study drug administration.

